#### Table 3.1 Documented Disease Progression and Censoring

Situation	Date of	Outcome
Inadequate baseline tumor assessment No on-treatment assessment and no death prior to first scheduled assessment	Randomization	Censored
Death or documented disease progression after ≥ 2 consecutively missed and/or not evaluable scheduled tumor assessments	Last tumor assessment documenting no disease progression	Censored
Alive, on-treatment, and no documented disease progression	Last tumor assessment documenting no disease progression	
Documented disease progression (on, prior to, or $\leq 30$ days after treatment discontinuation)	First tumor assessment documenting disease progression	Progression (Event)
New anticancer treatment $\leq$ 30 days after treatment discontinuation without disease progression	Last tumor assessment documenting no disease progression prior to starting the new anticancer treatment	Censored
Treatment discontinuation due to toxicity, undocumented disease progression, or any other reason	Last tumor assessment documenting no disease progression prior to discontinuation	Censored
Death prior to first scheduled assessment	Death	Death (Event)
Death without documented disease progression and $\leq 30$ days after treatment discontinuation	Death	Death (Event)

Note: Follow-up scans can be performed up to 4 weeks from last treatment dose date via protocol

## 3.2 Overall Survival

Overall Survival (OS) is defined as the time from randomization to the date of death for any cause. In the absence of confirmation of death, survival time will be censored at the last date the patient is known to be alive. Length of OS will be calculated in days and reported in months.

[Death/Censor Date - Randomization Date + 1] / 30.4375.

#### 3.3 Progression-Free Survival – Independent Radiologic Review

Independent radiologic review (IRR) will be performed using images from all available tumor assessments. PFS is defined as the number of months from the date of randomization to the date of death or documented (objective) disease progression via RECISTv1.1, whichever occurs earliest. Length of PFS will be calculated in days and reported in months.

[Progression/Death/Censor Date – Randomization Date + 1] / 30.4375.

Censorship rules for PFS per IRR will be defined the same as the investigator assessed.

## **3.4** Time to Progression

Time to Progression (TTP) will be derived using the investigator-assessed tumor assessment data. Censorship will occur for patients without documented disease progression. The last tumor assessment documenting no PD will be

Version Date: 29Jan2016

used as the date of event/censor. If death occurs prior to first tumor assessment the date of death will be used as the date of event/censor. Length of TTP will be calculated in days and reported in months.

[Progression/Censor Date - Randomization Date + 1] / 30.4375.

## 3.5 **Objective Response Rate**

Objective Response Rate (ORR) will be derived using the investigator-assessed tumor assessment data. Best Overall Response (BOR) is recorded from randomization until documented disease progression or death. ORR is defined as the proportion of patients with a BOR characterized as either a Complete Response (CR) or Partial Response (PR) as defined according to RECISTv1.1 guidelines relative to the total number of evaluable patients. Per RECISTv1.1 guidelines, patients with documented PR or CR will not need confirmatory tumor assessments to document response. Patients without baseline or post-baseline tumor assessments will be considered non-evaluable for this analysis. The following table describes the responder/non-responders for this analysis.

Table 3.5	ORR Determination
-----------	--------------------------

Criteria	Responder/Non- responder
No Baseline tumor assessment	Not Evaluable
No Post-baseline tumor assessment AND were treatment failure prior to BOR determination due to disease progression, symptomatic deterioration, toxicity, death, or new anticancer treatment	Non-Responder
BOR: Partial Response, Complete Response	Responder
AND were not treatment failure prior to BOR determination due to disease progression, symptomatic deterioration, toxicity, death, or new anticancer treatment	
BOR: Stable Disease, Progressive Disease, Not Evaluable/Indeterminate	Non-responder

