### 10.5.2. Secondary Efficacy Analysis

Overall Survival (OS) is defined as the time from the date of randomization to the date of death from any cause. Patients who are alive or lost to follow-up at the time of the analysis will be censored at the last known alive date. The majority of patients are expected to live at least 2 years, therefore the proportion of deaths at the time of the PFS analysis will not be sufficient for formal hypothesis testing of OS at that time.

Various sensitivity analyses will be performed on PFS and OS which will be further detailed in the SAP. PFS and OS will also be analyzed as an unstratified log-rank test for the primary and all sensitivity analysis as well. Other analyses include a PFS sensitivity analysis performed by declaring all censors as events and testing with a stratified log-rank.

Objective Response Rate (ORR) is defined as the proportion of patients with a RECIST v1.1 response recorded from randomization until disease progression characterized as either a Complete Response (CR) or Partial Response (PR) relative to the total number of evaluable patients. Frequency and percent will be as descriptive statistics while a Cochran-Mantel-Haenszel (CMH) test stratified by stratification factor will be tested. A chi-square test without stratification will also be presented. Frequency and percent along with 95% CI will be calculated

Time to Progression (TTP) is defined as the time from the date of randomization to the date of objective tumor progression. Those patients without objective tumor progression will be censored at the date of last tumor assessment documenting no objective progression. Patients who died prior to first scan will be censored on the date of death.

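### SAP 3.5 gives two rules for ORR patients with no post-baseline scan: the text drops them all, but Table 3.5 counts the treatment failures as non-responders

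*SAP*

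**What the plan says.** SAP 3.5 defines ORR as the share of patients whose best overall response (BOR) is CR or PR, with evaluable patients as the denominator. Two statements then say who is evaluable.

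- The text: "Patients without baseline or post-baseline tumor assessments will be considered non-evaluable for this analysis". It makes no exception for early failure.
- Table 3.5, which the next sentence introduces: "The following table describes the responder/non-responders for this analysis". Its Not Evaluable label goes only to "No Baseline tumor assessment". The next row, "No Post-baseline tumor assessment AND were treatment failure prior to BOR determination due to disease progression, symptomatic deterioration, toxicity, death, or new anticancer treatment", is labelled Non-Responder. The last row, "BOR: Stable Disease, Progressive Disease, Not Evaluable/Indeterminate", is also a non-responder category.

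Protocol 10.5.2 uses the same kind of denominator, "relative to the total number of evaluable patients", without saying who is evaluable. SAP 5.5.3 lists the ORR comparisons (CMH, Pearson chi-square, relative risk, risk difference) but names no denominator.

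**The concern.** Take a patient with a baseline scan and no later scan who dies, deteriorates or starts another therapy early. The text puts this patient outside the denominator; the table puts the patient inside it as a non-responder. Two programmers could each follow the SAP and report different ORRs from the same data.

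The choice matters beyond tidiness. Having a post-baseline scan is something that happens, or does not, after randomisation. A denominator that requires it removes patients who cannot be responders, so the rate can only rise. If the removed share differs between arms, the relative risk moves even when the arms respond equally.

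The PFS rules do not make up for this. SAP 3.1 censors patients with no assessment after dosing at randomisation, unless they died before the first planned assessment. Under the ORR text, a living patient who stopped for toxicity and was never scanned would therefore add nothing to PFS or to ORR.

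**Working it through.** **Step 1. The two rules side by side (SAP 3.5)**

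| Patient | Text | Table 3.5 | Result |
|---|---|---|---|
| No baseline assessment | Outside the denominator | Not Evaluable, outside | Agree |
| Baseline present, no post-baseline assessment, treatment failure | Outside | Non-Responder, inside | Contradiction |
| Baseline present, no post-baseline assessment, not a treatment failure (e.g. withdrawal, loss to follow-up) | Outside | No explicit row; inside if BOR is set to Not Evaluable/Indeterminate | Unresolved |
| Post-baseline assessment present, BOR not evaluable | Not excluded | Non-responder, inside | Agree |

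The sentence could be read as covering only patients who lack both assessments. But the table makes a missing baseline alone Not Evaluable, so the natural reading is that lacking either one is enough.

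**Step 2. Effect on one arm**

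The documents give no assumed ORR and no rate of missing first scans, so there is no planned figure to reproduce. Let R be responders, n patients with a baseline assessment, and f early failures with no post-baseline scan. None of the f can be among the R.

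- Table rule: R/n
- Text rule: R/(n - f)
- Ratio, text to table: 1/(1 - f/n)

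For an assumed f/n of:

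- 5%: 1/0.95 = 1.053, or 5.3% higher
- 10%: 1/0.90 = 1.111, or 11.1% higher
- 15%: 1/0.85 = 1.176, or 17.6% higher

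The ratio depends on f/n only, so it holds for the protocol's 80 patients randomised 1:1 (protocol 10.2) and for the 286 at 2:1 in SAP 5.1.

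**Step 3. Effect on the comparison**

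Illustration with the protocol's size, 80/2 = 40 per arm. Assumed: 8 responders in each arm, and 2 v 6 early failures without a scan.

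- Table rule: 8/40 = 20.0% in both arms, difference 0
- Text rule: 8/38 = 21.05% v 8/34 = 23.53%, difference 2.48, i.e. 2.5 points, in favour of the arm with more early failures

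The standard error of that difference is √(0.2105 × 0.7895/38 + 0.2353 × 0.7647/34) = 0.098, or 9.8 points. The shift is about a quarter of one standard error.

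On the ratio scale, assume a 15% response rate in both arms:

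- Early failure 5% v 15%: 0.15/0.95 = 15.8% v 0.15/0.85 = 17.6%, relative risk 0.95⁻¹ × 0.85 = 0.89
- Early failure 15% v 5%: 17.6% v 15.8%, relative risk 1.12
- Table rule in both cases: relative risk 1.00

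**Step 4. How many patients could be affected**

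Protocol 4.4 asks for a scan when treatment stops and again 8 weeks later. Footnote 5 of protocol 6.1 repeats the discontinuation scan for patients who stop for reasons other than progression, and continues scans every 8 weeks until progression. Protocol 7.7 adds an unscheduled assessment when progression is suspected. The SAP sentence asks for a post-baseline scan, not an on-treatment one, so a scan at discontinuation keeps the patient evaluable under either rule. The group left exposed is mainly deaths before any scan, withdrawals and missed scans.

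**The case against.** The strongest defence is that the table is the more specific rule. The text hands classification to Table 3.5, which keeps early failures in the denominator. The general sentence would then govern only patients with no scan and no treatment failure, and the conflict over early failures would not arise. That is a workable reading, and may be what was meant. But the SAP does not state it, and it still leaves a group excluded because of something that happened after randomisation.

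A reader might infer that patients who stop seribantumab early for toxicity would vanish from the response analysis, so that the randomised comparison is broken in that drug's favour. The documents do not support this. The scans required at discontinuation would keep most such patients evaluable. Nor is the direction known: in the earlier exemestane study (protocol 1.5.3.1) diarrhea was more frequent with seribantumab (50.0% v 23.7%), but serious adverse events were less frequent (12.5% v 18.6%).

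A reader might also infer that only an all-randomised denominator will do. Both documents specify evaluable patients, and a denominator limited to patients with an adequate baseline assessment also avoids selection on post-baseline events. The contradiction does not by itself require the wider choice.

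It is also fair to say that the 2 v 6 split is assumed, that the resulting shift is small beside the sampling error, and that the trial is sized on PFS. These points limit the consequence; they do not remove the contradiction. The SAP also names a different protocol number and a phase 3 design. That is a separate matter, and the undefined term in protocol 10.5.2 remains whichever SAP applies.

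**Conclusion.** The contradiction is certain from SAP 3.5 alone, and nothing elsewhere in the SAP or protocol settles it. If the text sentence is followed, ORR is conditioned on a post-randomisation event and is overstated by 1/(1 - f/n). The sizes, 5% to 18% in relative terms and 2.5 points between equal arms, are illustrations from assumed early-failure and response rates, not predictions. The true effect is probably smaller, because protocol-required scans should leave few patients without one. The direction of any bias between arms cannot be told from the documents. This is a correction that should be made to a secondary endpoint; it does not threaten the primary analysis.

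**What to change.** In SAP 3.5:

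1. Delete the reference to post-baseline assessments from the non-evaluable sentence, so that it concerns baseline only.
2. Change the second row of Table 3.5 so that any patient with no post-baseline assessment is a non-responder, whatever the reason. This also covers withdrawals and losses to follow-up, which have no row now.
3. State one denominator fixed by baseline status only: either all patients in the randomised analysis population, or those of them with an adequate baseline assessment. The second leaves the first row of Table 3.5 as it is; under the first, patients with no baseline assessment would become non-responders.

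Define evaluable in protocol 10.5.2 the same way at the next amendment. Protocol section 10 lets the SAP modify the planned analyses and ties amendments to major changes of the primary endpoint or its analysis, so the SAP correction need not wait. The protocol wording does need a written amendment (protocol 11.8).

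The cost is a few lines of SAP text, best settled before unblinding, and one line in a later amendment. ORR will be slightly lower than under the text rule. No extra data are needed.

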### Arm B (Comparator Arm):

- Placebo: intravenously (IV) on days 1 and 15 of each 28-day cycle
- Fulvestrant: 500 mg IM on days 1 and 15 of Cycle 1, and on day 1 of each subsequent 28 day cycle

Treatment must start within 7 days following randomization. It is intended that patients will be treated until investigator-assessed disease progression or unacceptable toxicity, whichever comes first. Tumor assessments will be measured and recorded by the local radiologist every 8 weeks (+/- 5 days) from randomization using the RECIST guidelines (version 1.1). Tumor assessments will be performed every 8 weeks regardless of dose delays or dose interruptions, until investigator-assessed progressive disease. Patients who come off study treatment prior to disease progression, for reasons including patient or physician decision or unacceptable toxicity, will continue to undergo tumor assessments every 8 weeks (±5 days) until investigator assessed PD. Patients will be treated according to local assessment of tumor scans, and the primary analysis will be conducted based on investigator assessments.

All patients will have a follow-up visit scheduled 30 days (±7 days) after the last dose of study treatment, regardless of reason for treatment termination. Patients will not be allowed to cross over from placebo to seribantumab.

Survival follow up will be required for all patients every 2 months from the 30-day follow-up visit until death, loss to follow-up, withdrawal of consent, or study termination. After patients discontinue study treatment, subsequent anti-cancer therapies will be collected at the same time as survival follow-up.

An independent data monitoring committee (DMC) will be established to monitor emerging safety data and evaluate for trial efficacy. The DMC will regularly monitor safety data over the course of the study in accordance with the DMC Charter.

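### SAP 3.5 defines ORR in two ways: its text runs to progression or death, while Table 3.5 adds an undefined treatment-failure condition and leaves some patients without a category

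*SAP*

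**What the plan says.** Protocol 10.5.2 defines ORR as "the proportion of patients with a RECIST v1.1 response recorded from randomization until disease progression", with CR or PR as the qualifying responses and evaluable patients as the denominator.

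The running text of SAP 3.5 sets nearly the same window: "Best Overall Response (BOR) is recorded from randomization until documented disease progression or death". Its numerator is patients whose best overall response (BOR) is CR or PR. It treats anyone lacking a baseline or a post-baseline assessment as non-evaluable.

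Table 3.5, which the same section presents as the classification for this analysis, has four rows:

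- No baseline assessment: not evaluable.
- "No Post-baseline tumor assessment AND were treatment failure prior to BOR determination due to disease progression" (or another of the listed reasons): non-responder.
- BOR of CR or PR, provided the patients "were not treatment failure prior to BOR determination due to disease progression, symptomatic deterioration, toxicity, death, or new anticancer treatment": responder.
- "BOR: Stable Disease, Progressive Disease, Not Evaluable/Indeterminate": non-responder.

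On follow-up, Protocol 3.1 says that patients who leave treatment before progression "will continue to undergo tumor assessments every 8 weeks (±5 days) until investigator assessed PD". Protocol 7.7 repeats this. Later anticancer therapies are recorded during survival follow-up (Protocol 3.1 and 6.6). For PFS, the protocol synopsis censors at the last scan before a new anticancer therapy. SAP 3.1 does the same for a new therapy started within 30 days of stopping treatment.

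**The concern.** A secondary endpoint that will be tested between arms needs one rule for who counts as a responder and who is in the denominator. Here the text ends the window only at progression or death, while the table also disqualifies on toxicity, symptomatic deterioration and new therapy. Under the text, a response that first appears on the next drug can count for the randomised arm. Under the table it cannot count as a response, but the table does not say what it becomes. If this stays open, someone has to settle it while programming, possibly after seeing which patients are involved.

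**Working it through.** No arithmetic in the plan can be reproduced here, because neither document states an expected ORR or a power for it. The check is to pass each kind of patient through both rules in SAP 3.5.

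**Step 1. Classification, patients with a baseline scan**

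| Post-baseline scan | Treatment failure before BOR | BOR | SAP 3.5 text | Table 3.5 |
|---|---|---|---|---|
| yes | no | CR/PR | responder | responder |
| yes | no | SD/PD/NE | non-responder | non-responder |
| yes | yes | SD/PD/NE | non-responder | non-responder |
| yes | yes | CR/PR | responder | no row |
| no | yes | none | non-evaluable | non-responder |
| no | no | none | non-evaluable | no row |

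The last three lines disagree. In the fourth, the treatment-failure non-responder row does not apply because it requires that there be no post-baseline scan, and the other non-responder row lists only SD, PD and NE. Of the listed failure reasons, progression and death already close the window in the text. The conflict therefore comes from toxicity, symptomatic deterioration and new anticancer therapy.

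**Step 2. Can the fourth line occur?** Yes. Protocol 3.1 and 7.7 keep 8-weekly scans going until progression after a stop for toxicity or by decision, so a first CR/PR can be recorded after the stop. Nothing in either section ends scanning when another therapy starts. That scans continue on the new therapy is inferred from this silence; it is not stated.

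**Step 3. Size of one patient.** Protocol 10.2 plans 80 patients randomised 1:1, so 80 / 2 = 40 per arm. Assuming all 40 are evaluable, one patient is 1 / 40 = 2.5 points of that arm's ORR.

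**Step 4. Illustration (all counts assumed).** Take 8 CR/PR patients in an arm of 40, with 2 of them first responding after a treatment failure:

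- Text: 8 / 40 = 20.0%.
- Table, the two scored as non-responders: 6 / 40 = 15.0%.
- Table, the two dropped as unclassified: 6 / 38 = 15.8%.

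For the denominator, take 8 responders and 2 patients with no post-baseline scan who failed treatment. The table gives 8 / 40 = 20.0% and the text 8 / 38 = 21.1%.

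With 4 to 12 responders and 1 to 4 post-failure responses, the gap between text and table runs from 1.8 points (30.0% against 11 / 39 = 28.2%) to 10 points (4 of 40 rescored).

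**Step 5. Against sampling error.** The SE of the difference between arms is sqrt(2 x p(1 - p) / 40): 6.7 points at an assumed ORR of 10% and 8.0 at 15%. One rescored patient is 2.5 / 6.7 = 0.37 or 2.5 / 8.0 = 0.31 of an SE.

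**The case against.** The strongest reply is that the table is the operational rule and simply refines the general text. A CR/PR patient who fails its condition would then naturally be a non-responder, and the missing row is only a drafting gap. Protocol section 10 also lets the SAP modify the protocol's plans and requires an amendment only for major changes to the primary endpoint or its analysis. This disposes of the protocol-versus-SAP difference as an error in itself. It does not remove the conflict inside SAP 3.5, where text and table put the same patient in different categories and the natural reading is not written down.

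It can also be said that few late responses would be seen. Protocol 4.4 mentions a scan at discontinuation and one 8 weeks later, and a note to SAP Table 3.1 allows follow-up scans up to 4 weeks after the last dose. That may limit the number, but a first CR/PR can still fall inside those periods.

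A reader might infer several stronger points that the documents do not support:

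- **A known bias against or for seribantumab.** Protocol 5.2.5.1 expects mainly low-grade events and a slight rise in grade 3 diarrhea or hypokalemia, generally well controlled. It says nothing about more discontinuations. Protocol 1.5.3.1 expects no rise in severe or serious events and reports SAEs in 12.5% with seribantumab plus exemestane against 18.6% in controls.
- **That the text counts every response whatever its quality.** The point concerns timing only. Protocol 7.7 asks for a repeat assessment at least 30 days later for a confirmed CR/PR, while SAP 3.5 requires none. That is a separate conflict.
- **That the table certainly removes responses seen at the discontinuation scan after a toxicity stop.** This depends on what treatment failure and BOR determination mean, and neither is defined. A response documented before the stop would not be affected.

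**Conclusion.** The point holds as an inconsistency of definition. SAP 3.5 gives ORR two incompatible response windows and two treatments of patients without a post-baseline scan, and it leaves two patient types without a row. Protocol 10.5.2 agrees with the SAP text on the window, apart from death, and so differs from the table.

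Each CR/PR rescored as a non-response moves its arm's ORR by 2.5 points, assuming 40 evaluable patients per arm. How many patients are affected, and whether they fall mainly in one arm, cannot be derived from the documents; the multi-patient figures above are illustrations. The figure of 40 comes from the protocol. The SAP names a different protocol number and describes a phase 3 exemestane/fulvestrant trial of 286 patients randomised 2:1, a wider mismatch that this point does not try to resolve.

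ORR is a secondary endpoint with no stated power. The primary PFS analysis is not touched. The matter deserves correction before unblinding but does not threaten the trial's main conclusion.

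**What to change.** Write one rule and use it in Protocol 10.5.2, the SAP 3.5 text and Table 3.5:

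1. Take BOR from randomization to the first of documented progression, death or start of a new anticancer therapy. This matches the principle already used for PFS, where follow-up is cut at new therapy.
2. Score a CR/PR first seen after a new anticancer therapy as a non-response, keep the patient in the denominator, and give this case its own row.
3. Make the responder row refer to that same window. Treat toxicity and symptomatic deterioration alike and consistently with the window; removing only one of them would leave text and table in conflict. If the term treatment failure is kept, define it.
4. Score patients with no post-baseline scan the same way in text and table, with or without treatment failure, for example as non-responders kept in the denominator.

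The cost is wording in two documents and a few lines of programming. Dates of new therapy and post-treatment scans are already to be collected. The reported ORR may be slightly lower than under the present protocol text.
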